11 STATISTICAL CONSIDERATIONS

11.1 Study Hypotheses

A formal hypothesis test is planned to compare nitazoxanide to placebo with respect to the primary efficacy outcome measure. The time from randomization until clinical resolution of Norovirus for at least 48 hours through 180 days will be compared between the two study arms.

The null hypothesis is that there is no difference in time until clinical resolution between study arms, with a two-sided alternative. The test for primary efficacy hypothesis will be conducted using a Log-Rank test at the 5% two-sided level of significance.

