Serum Immunoglobulin Testing (Serum total Ig and Norovirus-specific levels): Day 1 will assess baseline values, Day 28 will assess end of treatment levels. The proportion of subjects with ≥ 4 -fold rise in Norovirus-specific Ig titers from Day 1 will be assessed at Day 28 comparing

the nitazoxanide treatment group to the placebo group. In addition, the ratios of Norovirus-specific IgG to total IgG will also be compared between the nitazoxanide and placebo groups.

For exploratory outcome 22, an ANCOVA model will first be used to compare the treatment and placebo groups with respect to difference in changes of Norovirus-specific serum and stool IgA, IgM and IgG between Day 1 and Day 28 and between Day 1 and Day 60 (for stool only). A mixed effects model will then be used to compare the treatment and placebo groups with respect to difference in the changes of Norovirus-specific serum and stool IgA, IgM and IgG, which will use the longitudinal data observed at all three time points.

For exploratory outcomes 23-26, a Fisher's Z-transformation will be applied to the Pearson correlations between change in total lymphocyte count and T cell subsets at Day 1 and 180 and clinical resolution of symptoms in both the treatment and placebo groups, which will then be compared using a Z-test.

Pharmacokinetics and Dose Response:

For exploratory outcome 27, plasma concentrations of nitazoxanide metabolites in subjects consenting for PK blood draws at two time points will be described and summarized. Descriptive statistics (e.g. n, mean, standard deviation, % CV, median, and range) will be calculated for each sampling time.

Cox proportional hazard regression models will be used to examine the dose response relationship of Day 7 and Day 21 nitazoxanide metabolite concentrations on time from randomization until initial clinical resolution of Norovirus symptoms for at least 48 hours through Day 180. Additional analyses of PK endpoints may be described in the SAP.

Natural History of Disease:

Exploratory outcomes 28-31 are all time-to-event outcomes. They will be analyzed similarly as exploratory outcome 1.

Exploratory outcome 32 will be assessed similarly to exploratory outcome 14.

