3. STUDY OBJECTIVES AND ENDPOINTS

3.1. Study Objectives

3.1.1. Primary Objective:

- To assess the clinical efficacy of nitazoxanide for the management of acute and chronic Norovirus in transplant recipients.

3.1.2. Secondary Objectives:

- To assess the virologic efficacy of nitazoxanide.
- To assess the safety of nitazoxanide for the management of acute and chronic Norovirus in transplant recipients.

3.1.3. Exploratory Objectives:

- To assess initial clinical improvement in Norovirus Disease through 28 and 180 days.
- To assess markers of virologic improvement in Norovirus Disease through 28 and 180 days.
- To assess the contribution of immunologic response to Norovirus to the clinical course of disease in treated and untreated subjects.
- To define the pharmacokinetics and dose response relationships of nitazoxanide.
- To define the natural history of Norovirus in nitazoxanide treated and untreated subjects.

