- Time from randomization until initial clinical resolution of Norovirus symptoms for at least 48 hours through Day 180. Clinical resolution will be assessed from the daily diary by the subject and will be defined as cessation of vomiting and no stools classified by the Bristol Stool Chart as diarrhea (Type 6

or 7) from the total population compared to the subgroup of subjects who do not report chromaturia (discoloration of urine) based on unsolicited self-reporting.

- Incidence of unsolicited non-serious adverse events through 60 days, laboratory adverse events (WBC, Hemoglobin, Platelet Count, Creatinine, Alkaline Phosphatase, ALT, AST, BUN, and Bilirubin) through 60 days, protocol-specified serious adverse events through 60 days, and hospitalization through 60 days from the total population compared to the subgroup of subjects who do not report chromaturia (discoloration of urine) based on unsolicited self-reporting
- Time to ≥ 1 log reduction in stool Norovirus genome copies.
- Change in quantitative Norovirus load in the stool between Day 1 and Day 7, 14, 21, 28, 60, 120, and 180.
- Change in Norovirus sequence from Day 1 to Days 28 and 60.
- The effect of co-pathogens, as determined by the BioFire stool pathogen screen, on the time from randomization to first negative viral load through 180 days.
- Time from randomization to first negative viral load through 180 days and the change in viral titer between Day 1 and 180 from the total population compared to the subgroup of subjects who do not report chromaturia (discoloration of urine) based on unsolicited self-reporting.
- Change in Norovirus-specific serum and stool IgA, IgM and IgG between Day 1 and Days 28 and 60.
- Association between change in total lymphocyte count and T cell subsets at Day 1 and 180 and clinical resolution of Norovirus symptoms.
- Association between change in total lymphocyte count and T cell subsets at Day 1 and 180 and undetectable quantitative norovirus PCR.
- Association between change in Norovirus-specific serum and stool IgA, IgM and IgG from Day 1 to Days 28 and 60 and clinical resolution of Norovirus symptoms.
- Association between change in Norovirus-specific serum and stool IgA, IgM and IgG from Day 1 to Days 28 and 60 and undetectable quantitative Norovirus PCR.

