In this model, the expected serum IgA for the placebo group on Day 1 is β_0 , and on Day 28 ($t=28$) is $\beta_0 + \beta_2$. Therefore, the expected change from time Day 1 to Day 28 is β_2 for the placebo group. The expected serum IgA for the nitazoxanide group on Day 1 is $\beta_0 + \beta_1$, and on Day 28, it is $\beta_0 + \beta_1 + \beta_2 + \beta_3$. Therefore, the expected change for the nitazoxanide group from Day 1 to Day 28 is $\beta_2 + \beta_3$. Thus, the difference in rate of change in Norovirus-specific serum IgA from Day 1 to Day 28 between nitazoxanide and placebo groups is, on average, β_3 . The interpretation for parameter β_5 is similar.

The analyses will be performed on the Immunogenicity population. [Table 40](#) will present the coefficient estimates for the mixed effects model for the Norovirus-specific serum IgA assay. [Table 41](#), [Table 42](#), [Table 43](#), [Table 44](#), and [Table 45](#) will present the coefficient estimates for the mixed effects models for the remaining assay types.

The relationship between change in total lymphocyte count between Day 1 and 180 and the day of initial clinical resolution of symptoms will be evaluated using Pearson correlations. A Fisher's Z-transformation will be applied to the Pearson correlations in both the nitazoxanide and placebo groups. These will then be compared using a Z-test and the p-value will be reported along with the Pearson correlations and 95% confidence intervals in [Table 46](#). The following relationships will also be evaluated in [Table 46](#):

- Change in T cell subsets between Day 1 and 180 and the day of initial clinical resolution of symptoms.
- Change in total lymphocyte count between Day 1 and 180 and the first day of undetectable quantitative Norovirus PCR (see viral load in Section 3.3).
- Change in T cell subsets between Day 1 and 180 and the first day of undetectable quantitative Norovirus PCR (see viral load in Section 3.3).

Similarly, [Table 47](#) will evaluate the following relationships:

- Change in Norovirus-specific serum and stool IgA, IgM, and IgG from Day 1 to Day 28 and the day of initial clinical resolution of symptoms.
- Change in Norovirus-specific serum and stool IgA, IgM, and IgG from Day 1 to Day 60 and the day of initial clinical resolution of symptoms.
- Change in Norovirus-specific serum and stool IgA, IgM, and IgG from Day 1 to Day 28 and the first day of undetectable quantitative Norovirus PCR (see viral load in Section 3.3).

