Table 41: Mixed Effects Model Coefficient Estimates – Norovirus-Specific Stool IgA, Immunogenicity Population

Table 42: Mixed Effects Model Coefficient Estimates – Norovirus-Specific Serum IgG, Immunogenicity Population

Table 43: Mixed Effects Model Coefficient Estimates – Norovirus-Specific Stool IgG, Immunogenicity Population

Table 44: Mixed Effects Model Coefficient Estimates – Norovirus-Specific Serum IgM, Immunogenicity Population

Table 45: Mixed Effects Model Coefficient Estimates – Norovirus-Specific Stool IgM, Immunogenicity Population

Table 46: Correlation of Change in T-Cell Subset from Day 1 to Day 180 vs Clinical Resolution of Symptoms and Negative PCR by Treatment Group – Immunogenicity Population

T-Cell Subset	First Day of Clinical Resolution			First Day with Negative PCR		
	Pearson Correlation (95% CI)		P-value	Pearson Correlation (95% CI)		P-value
	Nitazoxanide 500 mg	Placebo		Nitazoxanide 500 mg	Placebo	
Total Lymphocyte Count	x.xx (x.xxxx, x.xxxx)	x.xx (x.xxxx, x.xxxx)	0.xxx	x.xx (x.xxxx, x.xxxx)	x.xx (x.xxxx, x.xxxx)	0.xxx
CD3+ Cells	x.xx (x.xxxx, x.xxxx)	x.xx (x.xxxx, x.xxxx)	0.xxx	x.xx (x.xxxx, x.xxxx)	x.xx (x.xxxx, x.xxxx)	0.xxx
CD3+ Cells/Lymphocytes	x.xx (x.xxxx, x.xxxx)	x.xx (x.xxxx, x.xxxx)	0.xxx	x.xx (x.xxxx, x.xxxx)	x.xx (x.xxxx, x.xxxx)	0.xxx
CD4+ Cells	x.xx (x.xxxx, x.xxxx)	x.xx (x.xxxx, x.xxxx)	0.xxx	x.xx (x.xxxx, x.xxxx)	x.xx (x.xxxx, x.xxxx)	0.xxx
CD4+ Cells/Lymphocytes	x.xx (x.xxxx, x.xxxx)	x.xx (x.xxxx, x.xxxx)	0.xxx	x.xx (x.xxxx, x.xxxx)	x.xx (x.xxxx, x.xxxx)	0.xxx
CD8+ Cells	x.xx (x.xxxx, x.xxxx)	x.xx (x.xxxx, x.xxxx)	0.xxx	x.xx (x.xxxx, x.xxxx)	x.xx (x.xxxx, x.xxxx)	0.xxx
CD8+ Cells/Lymphocytes	x.xx (x.xxxx, x.xxxx)	x.xx (x.xxxx, x.xxxx)	0.xxx	x.xx (x.xxxx, x.xxxx)	x.xx (x.xxxx, x.xxxx)	0.xxx

Table 47: Correlation of Change in Norovirus-Specific Immunoglobulin Assays vs Clinical Resolution of Symptoms and Negative PCR by Study Day and Treatment Group – Immunogenicity Population

Norovirus-Specific Assay	First Day of Clinical Resolution			First Day with Negative PCR		
	Pearson Correlation (95% CI)		P-value	Pearson Correlation (95% CI)		P-value
	Nitazoxanide 500 mg	Placebo		Nitazoxanide 500 mg	Placebo	
Serum IgA (Day 28)	x.xx (x.xxxx, x.xxxx)	x.xx (x.xxxx, x.xxxx)	0.xxx	x.xx (x.xxxx, x.xxxx)	x.xx (x.xxxx, x.xxxx)	0.xxx
Serum IgA (Day 60)	x.xx (x.xxxx, x.xxxx)	x.xx (x.xxxx, x.xxxx)	0.xxx	x.xx (x.xxxx, x.xxxx)	x.xx (x.xxxx, x.xxxx)	0.xxx

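### The only p-value for the immune-association outcomes (23-26) tests whether the correlation differs between arms; no combined estimate or test of the association itself is planned

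*SAP*

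**What the plan says.** The outcomes are worded as associations. The first in the SAP (3.2.4; number 23 in protocol 3.2.3) reads "Association between change in total lymphocyte count and T cell subsets at Day 1 and 180 and clinical resolution of Norovirus symptoms". The other three follow the same pattern, with undetectable PCR as the second variable or norovirus-specific immunoglobulins as the first. None names a comparison between arms. The parent objective (SAP 3.1) is "To assess the contribution of immunologic response to Norovirus to the clinical course of disease in treated and untreated subjects".

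For the analysis, SAP section 10 says the relationship "will be evaluated using Pearson correlations", transforms the correlation in each arm with Fisher's Z, and continues: "These will then be compared using a Z-test and the p-value will be reported along with the Pearson correlations and 95% confidence intervals". Protocol 11.4.5 has the same test, with correlations "in both the treatment and placebo groups, which will then be compared using a Z-test".

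The shell for Table 46, "Correlation of Change in T-Cell Subset from Day 1 to Day 180 vs Clinical Resolution of Symptoms and Negative PCR by Treatment Group", gives a correlation with 95% CI for each arm and one p-value per row and endpoint. Table 47 has the same layout for the immunoglobulins. Neither shell says what the p-value tests. The footnotes to Tables 33 and 39, by contrast, identify theirs as tests of between-treatment difference.

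**The concern.** The question asked is whether immune change and recovery go together. The hypothesis tested is whether they go together to the same degree in the two arms. If immune recovery helps clear the virus to a similar degree with and without nitazoxanide, the two correlations are equal and the between-arm null is true. The p-value is then uninformative about the association.

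Table 46 has 7 rows by 2 endpoints and Table 47 has 12 rows by 2 endpoints, so 14 + 24 = 38 p-values are planned. None of them tests for an association. Each sits in a column headed only as a p-value, next to two correlations, so a large value can be taken to mean that immune response and recovery are unrelated. A small value does not answer the outcome either: it says that the arms differ, not that an association exists in each. Finally, with 31 subjects enrolled, reading the association only from half-samples gives up precision that a combined estimate would keep.

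**Working it through.** The documents state no power, sample size or error rate for this analysis, so there is no planned figure to reproduce.

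**Inputs**
- Allocation 1:1 (SAP 4.4.3); 31 enrolled (SAP 14.2). The arm split is not given. I assume 16/15 at most, 10/10 as a lower case because not everyone will have both measurements, and 80/80 as originally planned.
- Alpha: not stated for this Z-test. I assume 0.05 two-sided. The level that protocol 11.1 states is for the primary test, "conducted using a Log-Rank test at the 5% two-sided level of significance".
- True correlation ρ: not given. I use 0.3, 0.5 and 0.7 in both arms, and the unequal pairs 0.6/0.3 and 0.8/0.4.

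**Formulas** (r is the arm's correlation and n its size; reject if the absolute value exceeds 1.96)
- Planned between-arm test: (atanh r₁ − atanh r₂) / √(1/(n₁−3) + 1/(n₂−3)). Null: ρ₁ = ρ₂.
- One arm's 95% CI excludes zero: atanh r × √(n−3). Null: ρ = 0 in that arm.
- Combined within arms: [(n₁−3) atanh r₁ + (n₂−3) atanh r₂] / √(n₁+n₂−6). Null: common ρ = 0.

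**Worked case: 16/15, ρ = 0.5 in both arms** (atanh 0.5 = 0.549)
- Between-arm: expected numerator 0, so rejection is 5.0%. This does not depend on ρ or n.
- Arm of 16: 0.549 × √13 = 1.98, power 51%. Arm of 15: 0.549 × √12 = 1.90, power 48%.
- Combined: 0.549 × √25 = 2.75, power 78%.

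**Equal correlations in both arms (normal approximation)**

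| n per arm | ρ | Between-arm Z-test | One arm's CI excludes 0 | Combined test |
|---|---|---|---|---|
| 16/15 | 0.3 | 5% | 20% / 19% | 34% |
| 16/15 | 0.5 | 5% | 51% / 48% | 78% |
| 16/15 | 0.7 | 5% | 88% / 85% | 99% |
| 10/10 | 0.3 | 5% | 13% | 21% |
| 10/10 | 0.5 | 5% | 31% | 54% |
| 10/10 | 0.7 | 5% | 63% | 90% |
| 80/80 | 0.3 | 5% | 78% | 97% |
| 80/80 | 0.5 | 5% | 99.8% | about 100% |

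Simulation of bivariate normal data (100,000 trials per setting at the two smaller sizes) agrees. At 16/15 and ρ = 0.5: between-arm 5.0%, single arm 53% and 50%, combined 81%. At 16/15 and ρ = 0.3: 5.1%, 21% and 20%, 36%. At 10/10 and ρ = 0.5: 4.9%, 33%, 59%. With ρ = 0 the combined test rejects 5.0% at both sizes.

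**Unequal correlations: rejection by the planned between-arm test**

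| ρ in the two arms | 10/10 | 16/15 | 80/80 |
|---|---|---|---|
| 0.6 / 0.3 | 11% | 16% | 66% |
| 0.8 / 0.4 | 24% | 39% | 99% |

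**The case against.** **The intervals already give inference.** A per-arm 95% CI that excludes zero is a 5% test of no association in that arm, and both intervals are reported. This stands. A reader might infer that the plan never assesses the association, and the documents do not support that. What is missing is a combined estimate and its p-value. Looking for either interval to exclude zero is not a full substitute: at 16/15 and ρ = 0.5 it succeeds in 77% of simulated trials, but at ρ = 0 it errs in 10% (1 − 0.95² = 9.75%).

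**The between-arm contrast serves a stated aim.** The objective covers treated and untreated subjects, and protocol 2.3.2 expects immune markers to help separate the role of host response from that of therapy. If the drug clears virus independently of immunity, the correlation should differ by arm. This also stands, so the Z-test should be kept. Nor does the protocol background on T cells and clearance (2.1) predict equal strength in both arms; equality is a scenario here, not a claim of the protocol.

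**Two further readings go too far.** One is that any association present in both arms is missed 95% of the time. That holds only for equal strengths, as the second table shows. The other is to treat the gap between 5% and 78% as lost power. Those tests have different nulls. The fair comparison is combined test against single-arm interval, which in the first table at 10/10 and 16/15 is a gain of 8 points (10/10, ρ = 0.3) to 31 points (16/15, ρ = 0.5, against the arm of 15).

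**The stakes are low.** The outcomes are exploratory, SAP 14.2 calls its revised analyses mainly descriptive, and both correlations with their intervals stand beside each p-value. That limits the consequence. It does not explain why the one test printed is for a different question, and a descriptive aim favours a combined estimate.

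**Conclusion.** The mismatch is real and appears in both documents: outcomes 23-26 are associations, and their only p-value tests equality between arms. For an equally strong association that p-value stays at its 5% error rate at any size, so early closure did not cause the problem and full enrolment would not have cured it.

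At the enrolled size, adding a combined analysis would raise the chance of detecting a common correlation of 0.5 from about 50% to 78-81% at 16/15, and from 31-33% to 54-59% at 10/10. At 0.3 and 16/15 it would rise from about 20% to about 35%, which is still low.

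These figures rest on two-sided alpha 0.05, the assumed arm sizes and correlations, bivariate normality and a correlation common to both arms. The direction of the conclusion needs only that the two nulls differ. The point is worth acting on because the change is cheap, not because a main conclusion of the trial depends on it.

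**What to change.** In SAP section 10 and Tables 46 and 47:

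1. Add a treatment-stratified correlation: combine the arms on the Fisher z scale with weights n−3, back-transform, and give the 95% CI and a p-value for no association.
2. Keep the between-arm Z-test, and label its p-value in the column heading and a footnote as a test of between-arm difference in correlation (effect modification).
3. As the study is closed, record this in the SAP and the clinical study report as a change from the analysis in protocol 11.4.5, where the arms are estimated separately and "which will then be compared using a Z-test".

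The cost is a few lines of text and an added estimate and p-value per endpoint in two tables; no new data are needed. There are two downsides. It adds 38 exploratory p-values with no multiplicity adjustment (SAP 6.8 plans none). The combined estimate also assumes a common correlation, which the Z-test can hardly check at this size: it detects 0.6 against 0.3 in only 11-16% of trials. Correlations of opposite sign would cancel: at 0.5 and −0.5 with 16/15 the combined test rejects 5% and the Z-test 78%. The per-arm results should therefore stay in the tables.

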11. OTHER ANALYSES

The protocol calls for a Log-Rank test at the 5% two-sided level of significance for the following outcome measures:

- Time to allograft rejection as per each center team.
- Time to graft loss as reported to UNOS.
- Time to death.
- Time to withdrawal from the study because of intolerance or drug related adverse events.

However, due to early closure of the study, the number of subjects is too small to use a Log-Rank test. Instead, a stratified Cox proportional hazards model will be used to compare treatment to control through Day 180. Stratification is based on acute versus chronic symptoms at baseline. No pediatric subjects were enrolled in the study and only one hematopoietic stem cell transplant subject was enrolled in the study; therefore, the transplant type and age range strata will not be included in the final analysis.

The analysis will be performed in the mITT analysis population. The treatment hazard ratio estimate, 95% confidence interval and p-value from the likelihood ratio test will be presented for each event ([Table 108](#)). The median time to event and 95% confidence interval will be summarized by treatment arm and duration of symptoms. In addition, stratum-specific estimates of the treatment hazard ratio within each duration of symptoms strata will be presented. Kaplan-Meier curves for each treatment arm will be displayed in [Figure 27](#), [Figure 28](#), [Figure 29](#), and [Figure 30](#). A listing of graft loss and rejection is presented in [Listing 29](#) and a listing of deaths is presented in [Listing 30](#).

The primary analysis will be repeated on the mITT population using secretor status as defined by phenotype and genotype, separately ([Table 48](#)). Individual secretor status data is presented in [Listing 19](#).

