Pharmacokinetics and Dose Response:

27. For subjects consenting to PK draws, concentrations of nitazoxanide metabolites (tizoxanide and tizoxanide glucuronide) 1 to 4 hours after the first dose on Day 7 and 10 minutes before the second dose on Day 21.

Natural History of Disease:

28. Time to allograft rejection as per each center team
29. Time to allograft loss as reported to UNOS.
30. Time to death.
31. Time to withdrawal from the study because of intolerance or drug related adverse events.
32. Correlation of secretor status as defined by phenotype and genotype, separately, and clinical resolution of Norovirus as defined by the primary endpoint.

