3.2.4. Exploratory Outcome Measures

- Time from randomization to initial clinical improvement in Norovirus disease through 28 and 180 days for at least 48 hours, as defined by:
 - 50% reduction in number of episodes of vomiting and,
 - Improvement in PO intake, as judged by the subjects and,
 - 50% reduction in the number of episodes of diarrhea as classified by the subject by the Bristol Stool Chart as type 6 or 7 bowel movements.
- Time from randomization to initial cessation of vomiting through Day 180 (recurrent vomiting will be considered disease recurrence unless determined to be due to another etiology [i.e. GVHD]).
- Time from randomization to subject report of no loss of appetite that is maintained for 48 hours through Day 180 (measure will be first time that the subject reports that they have no “loss of appetite” on their daily diary).
- Time from first dose to initial cessation of diarrhea through Day 180 classified by the Bristol Stool Chart as type 6 or 7 bowel movements (recurrent diarrhea will be considered disease recurrence unless determined to be due to another etiology [i.e. GVHD]).
- Time from randomization to 50% reduction in the amount of antimotility agents utilized by the subject through Day 180.
- Number of days of diarrhea through Days 28 and 180.
- Number of stools classified by the Bristol Stool Chart as type 6 or 7 bowel movements through Day 28.
- Number of days of IV hydration or total parenteral nutrition (TPN) therapy through Day 28.
- Total number of days of hospitalization through Days 28 and 180.
- Change in patient-reported quality of life as measured by EuroQOL-5 (global) and IBSQOL (diarrhea specific) [adult] or EuroQOL-5 Peds (global) and PedsQL GI Module [children] from baseline to Day 180.
- Change in patient-reported physical function as measured by NIH PROMIS Physical Function (Adult) Pediatric Global Health (Peds) from baseline to Day 180.
- Change in patient-reported emotional distress as measured by the NIH PROMIS Depression, Anxiety, Fatigue (Adult and Peds) from baseline to Day 180.
- Change in patient-reported gastrointestinal symptoms as measured by the NIH PROMIS GI (Adult and Peds) symptoms (6 of 8 subscales) from baseline to Day 180.
- The effect of co-pathogens, as determined by the BioFire stool pathogen screen, on the primary outcome measure.

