8. EFFICACY EVALUATION

All primary and secondary efficacy analyses will be conducted in the mITT and PP populations. Data will be summarized by treatment group with a column for each treatment in the order (Nitazoxanide, Placebo) and will be annotated with the total population size relevant to that table/treatment. Subgroups with less than five subjects per treatment group will be excluded from efficacy tables and figures. All efficacy variables will be listed by site, treatment group and subject, and when appropriate, by visit number within subject ([Listing 12](#), [Listing 13](#), [Listing 14](#), [Listing 15](#), [Listing 16](#), [Listing 17](#), [Listing 18](#), [Listing 19](#), and [Listing 22](#)).

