	Nitazoxanide 500 mg (N =X)	Day 180	x.x	x.x	x.x	x.x	x.x, x.x	0.xxx
	Placebo (N=X)		x.x	x.x	x.x	x.x	x.x, x.x	

Implementation note: Repeat for Physical Function, Depression, Anxiety, Fatigue, GI Symptoms: Diarrhea, GI Symptoms: Nausea, GI Symptoms: Fecal Incontinence, GI Symptoms: Belly Pain.

N = Number of subjects in the specified treatment group and analysis population with patient-reported measure on the given study day.

Note: Adjustments based on baseline mean values for each patient-reported measure.

P-value is the test of between-treatment differences for change in each patient-reported measure from baseline to Day 180.

Table 34: Time to Initial Clinical Resolution by Treatment Group and Co-Pathogen – mITT Population

Implementation Note: If an estimate is not calculable, insert “NC” in the cell and add a footnote “NC = Not calculable. If a subgroup has less than 5 subjects per treatment group, then remove rows and add footnote specifying which group(s) are excluded from analyses.”

Treatment Group	Co-Pathogens	n	Median Time to Initial Clinical Resolution		HR		P-value
			Estimate	95% CI	Estimate	95% CI	
Nitazoxanide 500 mg (N=X)	Present	X	X.X	X.X, X.X	X.XX	X.XX, X.XX	--
Placebo (N=X)		X	X.X	X.X, X.X			
Nitazoxanide 500 mg (N=X)	Absent	X	X.X	X.X, X.X	X.XX	X.XX, X.XX	--
Placebo (N=X)		X	X.X	X.X, X.X			
Nitazoxanide 500 mg (N=X)	Any Status	X	X.X	X.X, X.X	X.XX	X.XX, X.XX	0.xxx
Placebo (N=X)		X	X.X	X.X, X.X			

N = Number of subjects in the specified treatment group, co-pathogen status strata, and analysis population.

n = Number of subjects with initial clinical resolution of symptoms.

Note: HR is the ratio of the hazard of initial clinical resolution in each treatment group estimated from the Cox model. The ratio is Nitazoxanide 500 mg to Placebo.

HR for the ‘Any Status’ group is the hazard ratio from the stratified Cox Model.

P-value calculated using the likelihood ratio test.

Table 35: Time to First Negative Viral Load by Treatment Group and Co-Pathogen – Norovirus GII, mITT Population

Implementation Note: If an estimate is not calculable, insert “NC” in the cell and add a footnote “NC = Not calculable.” If a subgroup has less than 5 subjects per treatment group, then remove rows and add footnote specifying which group(s) are excluded from analyses.

Treatment Group	Co-Pathogens	n	Median Time to First Negative Viral Load		HR		P-value
			Estimate	95% CI	Estimate	95% CI	
Nitazoxanide 500 mg (N=X)	Present	x	x.x	x.x, x.x	x.xx	x.xx, x.xx	--

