Stool IgA (Day 28)	x.xx (x.xxxx, x.xxxx)	x.xx (x.xxxx, x.xxxx)	0.xxx	x.xx (x.xxxx, x.xxxx)	x.xx (x.xxxx, x.xxxx)	0.xxx
Stool IgA (Day 60)	x.xx (x.xxxx, x.xxxx)	x.xx (x.xxxx, x.xxxx)	0.xxx	x.xx (x.xxxx, x.xxxx)	x.xx (x.xxxx, x.xxxx)	0.xxx

Implementation note: Repeat for Serum IgG (Day 28), Serum IgG (Day 60), Stool IgG (Day 28), Stool IgG (Day 60), Serum IgM (Day 28), Serum IgM (Day 60), Stool IgM (Day 28), and Stool IgM (Day 60).

Note: Change in Norovirus-specific assay is the change Day 1 to the given study day (Day 28 or Day 60).

Table 48: Time to Initial Clinical Resolution by Test, Treatment Group and Secretor Status – mITT Population

Implementation Note: If an estimate is not calculable, insert “NC” in the cell and add a footnote “NC = Not calculable.” If a subgroup has less than 5 subjects per treatment group, then remove rows and add footnote specifying which group(s) are excluded from analyses.

Test	Treatment Group	Secretor Status	n	Median Time to Initial Clinical Resolution		HR		P-value
				Estimate	95% CI	Estimate	95% CI	
Genotype	Nitazoxanide 500 mg (N=X)	Secretor	x	x.x	x.x, x.x	x.xx	x.xx, x.xx	--
	Placebo (N=X)		x	x.x	x.x, x.x			
	Nitazoxanide 500 mg (N=X)	Non-Secretor	x	x.x	x.x, x.x	x.xx	x.xx, x.xx	--
	Placebo (N=X)		x	x.x	x.x, x.x			
	Nitazoxanide 500 mg (N=X)	Any Status	x	x.x	x.x, x.x	x.xx	x.xx, x.xx	0.xxx
	Placebo (N=X)		x	x.x	x.x, x.x			
Phenotype	Nitazoxanide 500 mg (N=X)	Secretor	x	x.x	x.x, x.x	x.xx	x.xx, x.xx	--
	Placebo (N=X)		x	x.x	x.x, x.x			
	Nitazoxanide 500 mg (N=X)	Non-Secretor	x	x.x	x.x, x.x	x.xx	x.xx, x.xx	--
	Placebo (N=X)		x	x.x	x.x, x.x			
	Nitazoxanide 500 mg (N=X)	Any Status	x	x.x	x.x, x.x	x.xx	x.xx, x.xx	0.xxx
	Placebo (N=X)		x	x.x	x.x, x.x			

N = Number of subjects in the specified treatment group and secretor status strata with valid results for the given test type.

n = Number of subjects with initial clinical resolution of symptoms.

Note: HR is the ratio of the hazard of initial clinical resolution in each treatment group estimated from the Cox model. The ratio is Nitazoxanide 500 mg to Placebo.

HR for the ‘Any Status’ group is the hazard ratio from the stratified Cox Model.

P-value calculated using the likelihood ratio test.

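### Table 48 has no hazard ratio for secretor versus non-secretor, and the shells for Tables 34–36 have no row for the co-pathogen effect that SAP 8.3 specifies

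*SAP*

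**What the plan says.** **Secretor status.** Protocol 3.2.3 lists outcome 32 as "Correlation of secretor status as defined by phenotype and genotype, separately, and clinical resolution of Norovirus as defined by the primary endpoint". Protocol 11.4.5 gives the method: "Exploratory outcome 32 will be assessed similarly to exploratory outcome 14". For outcome 14, the same section puts presence or absence of co-pathogens into a Cox model as a binary covariate, with a time-varying version as an alternative.

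SAP 11 reads: "The primary analysis will be repeated on the mITT population using secretor status as defined by phenotype and genotype, separately". The primary analysis in SAP 8.1 is a comparison of treatment with placebo. The Table 48 shell has rows for secretor, non-secretor and any status, separately for genotype and phenotype. Its footnote reads: "Note: HR is the ratio of the hazard of initial clinical resolution in each treatment group estimated from the Cox model", and the ratio is defined as nitazoxanide to placebo.

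**Co-pathogens.** SAP 3.2.4 lists "The effect of co-pathogens, as determined by the BioFire stool pathogen screen, on the primary outcome measure" and "The effect of co-pathogens, as determined by the BioFire stool pathogen screen, on the time from randomization to first negative viral load through 180 days". SAP 8.3 assigns these to Table 34 and to Tables 35–36. It says each time that co-pathogen status is a binary covariate in the Cox model, or time-varying if status changes often. The Table 34 shell counts subjects differently: "N = Number of subjects in the specified treatment group, co-pathogen status strata, and analysis population". Table 35 is laid out the same way and Table 36 follows its format. All three define the HR as nitazoxanide to placebo.

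All four shells also give the number with the event and the median time with 95% CI, by arm within each level of the factor.

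**Small cells.** SAP 8 adds: "Subgroups with less than five subjects per treatment group will be excluded from efficacy tables and figures".

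**The concern.** The three outcomes ask about the factor: do secretors resolve at a different rate from non-secretors, and do co-pathogens delay resolution or viral clearance? A treatment HR within each level answers another question, namely whether the drug effect differs by level. SAP 6.4 says the study was not powered for its subgroup analyses.

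For secretor status, a programmer who follows SAP 11 and the Table 48 shell will report outcome 32 without an estimate, interval or test for the association it names. SAP 11 explains why the four natural-history outcomes lose their log-rank test, but gives no reason for the change to outcome 32. SAP 14.2 offers only a general remark about small-sample and descriptive methods.

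For co-pathogens, text and shell point to different outputs. A programmer working from the shell would leave out the coefficient that the text calls for.

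**Working it through.** **Step 1. Set outcome, method and output side by side.**

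| | Outcome 32 (secretor) | Outcomes 14 and 20 (co-pathogen) |
|---|---|---|
| Quantity asked for | association of the factor with resolution | effect of the factor on resolution / first negative viral load |
| Protocol 11.4.5 | as outcome 14: binary Cox covariate | binary Cox covariate, time-varying if needed |
| SAP text | primary analysis repeated by status; no covariate named (SAP 11) | binary or time-varying covariate (SAP 8.3) |
| HRs in the shell | nitazoxanide to placebo only (Table 48) | nitazoxanide to placebo only (Tables 34–36) |
| Row for the factor's HR | none | none |

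For secretor status, text and shell both omit the estimate. For co-pathogens only the shell does. Fixed present/absent rows also cannot display a time-varying covariate, because a subject may belong to both rows over time.

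**Step 2. Could the factor's HR be read off the model behind the shell?** Not if the model is stratified by the factor, since such a Cox model has no coefficient for its stratifier. In simulated data (30 sets of 1,000 subjects, true treatment HR 2), the model stratified by the factor returned one parameter, the treatment HR: 2.04 when the true factor HR was 1, and 2.05 when it was 3. The model with the factor as a covariate returned factor HRs of 0.99 and 3.02. If the stratifier is symptom duration instead, the only HR the shell defines is still the treatment HR.

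**Step 3. How precise would the missing estimate be?** Inputs:
- 31 enrolled (SAP 6.6), taken as 15.5 per arm.
- Design medians of 135 and 67.5 days (SAP 5) and 180 days of follow-up. Exponential times and no dropout are assumptions.
- 70–80% secretors in general (Protocol 2.1), so 20–30% non-secretors.

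Event probabilities: 1 − 2^(−180/135) = 0.603 and 1 − 2^(−180/67.5) = 0.843.

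Expected events: 15.5 × (0.603 + 0.843) = 22.4.

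Standard error of the log HR: 1/√(events × q × (1 − q)), where q is the non-secretor share.

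| q | SE | 95% CI multiplies/divides the HR by exp(1.96 × SE) |
|---|---|---|
| 0.25 | 1/√(22.4 × 0.25 × 0.75) = 0.49 | 2.6 |
| 0.10 | 1/√(22.4 × 0.10 × 0.90) = 0.70 | about 4 |
| 0.05 | 1/√(22.4 × 0.05 × 0.95) = 0.97 | about 6.7 |

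**Step 4. Would the non-secretor rows of Table 48 survive the rule of five?** Assume arms of 15 and 16.

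| q | P(<5), n = 15 | P(<5), n = 16 | Either arm below five | Both arms below five |
|---|---|---|---|---|
| 0.20 | 0.836 | 0.798 | 1 − 0.164 × 0.202 = 0.97 | 0.836 × 0.798 = 0.67 |
| 0.30 | 0.515 | 0.450 | 1 − 0.485 × 0.550 = 0.73 | 0.515 × 0.450 = 0.23 |

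The SAP does not say whether one arm below five is enough or both must be. Deletion would also remove the non-secretor medians, which are the only descriptive comparison by status in the table.

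**The case against.** The best reply is that SAP 8.3 already specifies the right model for co-pathogens. This stands. A reader might infer from Tables 34–36 that the co-pathogen effect is never estimated. The documents do not support that: fitting the SAP 8.3 model yields the coefficient, and the fault is a mock-up without a row for it.

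Second, the shells do not consist only of treatment HRs. They give counts and medians with intervals by arm and status, and SAP 14.2 says the revised analyses will be primarily descriptive. This also stands, but medians within arms supply no between-status estimate or test.

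Third, a reader might take the overall row to come from a model stratified by the factor itself. The footnotes say only that the Cox model is stratified. The subject-count footnotes suggest the factor, while the primary model in SAP 8.1 is stratified by symptom duration. The stratifier is not named, and the point does not depend on it.

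Fourth, it is tempting to say that Table 48 will end up saying nothing about secretor status. That goes too far: the secretor rows may remain, and Listing 19 gives individual status. The deletion probabilities also rest on a general-population share. Protocol 2.1 says non-secretors are less susceptible to symptomatic infection, so the enrolled share may be lower. That makes deletion more likely and the pooled estimate less precise.

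Finally, these are exploratory outcomes in a trial stopped at 31 subjects. Even at a standard error of 0.49, 80% power needs an HR near 3.9 (exp(2.8 × 0.49)). This limits the importance of the point; it does not explain why the named quantity is left out.

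**Conclusion.** The point holds in two parts of different weight.

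- **Outcome 32:** SAP 11 and Table 48 replace the association asked for with a treatment comparison by secretor status. No HR, CI or p-value for secretor versus non-secretor would be produced, contrary to the method in Protocol 11.4.5.
- **Outcomes 14 and 20:** the SAP text is right and the shells for Tables 34–36 conflict with it, with no place for the co-pathogen HR.

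Both conclusions come from reading the documents and need no numerical assumption. The figures are illustrative. The standard error of about 0.49 assumes the design medians, exponential times, no dropout and 25% non-secretors; it rises to 0.70 at 10% and 0.97 at 5%. Loss of the non-secretor rows has a probability of 73–97% if one arm below five is enough, or 23–67% if both must be, assuming a 15/16 split and 20–30% non-secretors. No primary, secondary or safety conclusion changes.

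**What to change.** 1. In SAP 11, state that secretor status, by phenotype and genotype separately, enters a Cox model as a covariate alongside treatment, stratified by duration of symptoms.
2. Add to Table 48, for each test, a row with the secretor versus non-secretor HR, 95% CI and p-value.
3. Add the matching co-pathogen row (present versus absent) to Tables 34, 35 and 36. Keep the time-varying option of SAP 8.3 and enter NC where the model cannot be estimated. Table 36 is a likely case, because SAP 3.3 says GII predominates over GI.
4. Align the footnotes of all four tables with the text, and name the stratifier of the overall row.
5. Keep the treatment HRs by level, labelled as descriptive.

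The cost is one SAP sentence, four table shells and one additional model fit per factor and endpoint, using data already collected.
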